### 4.3.2 Premature Patient Withdrawal from Study Treatment

Patients may be withdrawn from study treatment for the following reasons:

- Occurrence of a condition or disease that interferes with the study treatment or represents an exclusion criterion.
- Administration of IVIG other than Panzyga. All patients who received at least one dose of the study treatment should be followed up per protocol until the study end without administration of the study product.

- Occurrence of an AE or SAE, which in the opinion of the investigator, precludes further treatment with study medication (Section 7.3.2).

If a patient shows worsening of their symptoms based on CGI-Improvement ratings, they will be presented to the site PI for review and treatment planning. Patients for whom worsening continues at a minimal level ("5" or "mildly worse") for an extended period of six weeks (2 visits) or moderately or greater level ("6" or "7"; much worse or very much worse) since last visit (up to three weeks) will be considered for premature withdrawal from the study drug and administration of appropriate standard of care treatment unless clinical interventions using approved study procedures and/or mediations have a reasonable likelihood to improve symptoms. Patients who experience an emergency worsening of symptoms may at the discretion of the site clinician be withdrawn from the study drug at any time to obtain necessary standard of care treatment. In addition, patients who develop exclusionary criteria (e.g. bipolar disorder, suicide attempt) will be withdrawn from the study drug and will receive appropriate standard of care treatment. All patients withdrawn from the study drug prematurely will be asked to continue the study as planned with modification of the study schedule (e.g. IMP administration and related to it safety lab tests will be omitted). Details of concomitant medications and procedures administrated per standard of care will be captured in patient case reports.

The eCRF will contain an End of Treatment and an End of Study page. The End of Treatment page will record whether the patient will be followed up per protocol, to allow for correct patient status tracking and to provide the reason for the drug withdrawal.

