8.3. Handling of Missing Data

For the primary efficacy analysis, missing CY-BOCS results at Week 9 will be subjected to the multiple imputation method assuming missing at random, to include all randomized patients into the analysis.

In an additional sensitivity analysis such missing primary endpoint data will be replaced with the median change observed in the placebo group.

In case of missing weight measurements the last available body weight will be used for calculations related to dosing. In individual patient data listings missing data will however not be replaced by imputed values.

Missing data in secondary analysis variables will not be replaced by any method of imputation; instead, the frequency of missing values will be presented.

For adverse events the following will be applied:

AEs will be reported from the moment that informed consent has been given throughout the complete observation period; AEs with onset after start of the first IMP administration will be considered to be 'treatment-emergent' with respect to the treatment group of the patient at time of onset as defined in section 8.4 below.

If the start date and time of an AE are partially or completely missing, the AE will be considered as treatment-emergent in the analysis if it cannot be definitely shown that the AE did not occur or worsen after first IMP administration (worst case approach). Missing dates and times will not be replaced.

For medications the following will be applied:

A medication will be assumed to be concomitant if it cannot be definitely shown that the medication was not administered after the first IMP administration. Missing dates will not be replaced.

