8.4. Derived and Computed Variables

The following derived/computed variables have been initially identified as important for the analysis of the primary and secondary target variables. It is expected that additional variables and flags will be required. The SAP will not be amended for additional variables that are not related to the primary target or key secondary target variables. Any additional derived or computed variables will be identified and documented in the SAS programs that create the analysis files. If the SAP is not amended, further derivations related to primary and secondary target variables will be described in the CSR.

- The age of a patient is defined according to the usual definition that a person is n years old until she or he has completed her or his (n+1)th year of life, using the date of informed consent as the reference date. This is also the definition that will be applied for evaluation of the age related inclusion criteria. [Unit: years]
- Body Mass Index: $BMI = (\text{Body weight}) / \text{Height}^2$ [Unit: kg/m^2]
- Treatment group for safety analyses: Because of the cross-over follow-up phase in this study, safety data will be summarized in 3 groups:
 1. 'Panzyga': Patients with either
 - Panzyga as the first IMP administered, from start of treatment and up to 21 days after the end of the last Panzyga infusion, or with
 - Panzyga as their 2nd treatment, from start of Panzyga treatment until the end of the observation period.
 2. 'Placebo': Patients with Placebo as their first IMP administered, from start of treatment until the first administration of Panzyga.
 3. 'Placebo after Panzyga': Patients who received Panzyga in the first period and are now treated with Placebo, from 22 days after the last Panzyga administration until the end of the observation period.

Derivations with respect to evaluation/scoring of the standardized assessment tools/questionnaires used in this study (CY-BOCS, CGI, COIS, SNAP-IV, PTQ, C-SSRS) will be done according to the respective scoring manuals and are therefore not detailed in this SAP.

Property of Octapharma. Do not copy or distribute without written permission.

9. Study Patients and Demographics

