10.3.3. Pediatric Patients with PANs improvement

PANS improvement will be defined as improvement of PANS symptoms based on CGI-I ratings at Week 9 since Week 3, and at Week 18 since Week 12. Patient will be evaluated as PANS improvement if the CGI-I score is 3 (Minimally Improved) or better at the evaluated visit.

The descriptive statistics (n and percentage %) for patients with PANS improvement will be summarized by treatment groups at Week 9 and Week 18.

not

11. Safety and Tolerability Analyses

The safety analysis will comprise descriptive statistics, tabulations and listings of all adverse events (AEs), safety laboratory results, and physical examination findings. The safety analysis will be made with the FAS, including all randomized patients who received at least part of one infusion of Panzyga or placebo. In the event that a patient received the wrong study drug (i.e. did not take the randomized study drug), the actual treatment will be used for safety analyses.

To account for the cross-over follow-up phase in this study, safety tabulations will differentiate between 3 patients groups according to their treatment status as defined in section 8.4 above.

In particular, AEs in patients with treatment sequence (Panzyga – Placebo) that start more than 21 days after the last administration of Panzyga will be reported separately, and an additional medical review will be performed to identify any possible signal of events with long latency.

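### SAP 8.4 gives no safety group for the time after study drug stops or non-study immunoglobulin is given, so some events after immunoglobulin count as placebo events

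*SAP*

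**What the plan says.** SAP section 11 states that "safety tabulations will differentiate between 3 patients groups according to their treatment status as defined in section 8.4 above". SAP 8.3 makes an event treatment-emergent "with respect to the treatment group of the patient at time of onset as defined in section 8.4 below". The windows in SAP 8.4 therefore decide the column for each event. They are:

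- *Panzyga*, Panzyga-first patients: "Panzyga as the first IMP administered, from start of treatment and up to 21 days after the end of the last Panzyga infusion".
- *Panzyga*, placebo-first patients: "Panzyga as their 2nd treatment, from start of Panzyga treatment until the end of the observation period".
- *Placebo*: "Placebo': Patients with Placebo as their first IMP administered, from start of treatment until the first administration of Panzyga".
- *Placebo after Panzyga*: "Patients who received Panzyga in the first period and are now treated with Placebo", from day 22 after the last Panzyga dose to the end of observation.

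Protocol 4.2.2 forbids other immunoglobulin, and says that a patient who receives it comes off study treatment. Protocol 4.3.2 lists the same event as a reason for stopping: "Administration of IVIG other than Panzyga. All patients who received at least one dose of the study treatment should be followed up per protocol", to study end and without study product. For stopping in general it says "All patients withdrawn from the study drug prematurely will be asked to continue the study as planned with modification of the study schedule".

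**The concern.** The *Placebo* window has one exit, the first Panzyga dose. Protocol 4.3.2 describes patients who never reach that exit yet stay under observation. If such a patient has been given another immunoglobulin, later events are counted in the saline column.

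Protocol 1.3 names thrombosis, renal failure and hemolysis as known risks of IVIG. Events of this kind in the comparator column shrink the difference that the safety tables are meant to show. The path is plausible: protocol 1.3 says that IVIG is recommended for moderate to severe PANS, which is the trial population, and 4.3.2 gives standard of care to patients who worsen and stop study drug.

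Two neighbouring gaps have the same cause. The second-period *Panzyga* window also has no end when study drug stops or other immunoglobulin is given. A Panzyga-first patient stopped before any saline is not being treated with placebo, so after day 21 that patient meets none of the three definitions as worded.

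**Working it through.** The documents state no figure for this point, so there is nothing to reproduce. The sample size is blacked out, so no patient numbers can be given. The check traces the wording and then gives three illustrations.

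**1. Trace of one patient.** A placebo-first patient receives cycles 1 and 2 and is then given non-Panzyga IVIG.

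- Protocol 4.2.2 and 4.3.2: off study treatment, followed to study end without study product.
- SAP 8.4: no Panzyga is given, so *Placebo* does not close.
- SAP 8.3: a later event takes the group at onset, which is *Placebo*.
- The actual-treatment rule in SAP 7 and 11 covers a patient who got the wrong study drug. Non-study IVIG is not study drug, so this rule does not move the event.

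**2. Length of the open window.** Inputs: three-week cycles of two infusion days, 18 weeks = 126 days (protocol 6.2.1), first infusion on day 0. The last infusion of cycle k falls on day 21(k − 1) + 1. The SAP sets a 21-day limit only for Panzyga-first patients; it is borrowed here for placebo. Time beyond it is 126 − [21(k − 1) + 1 + 21] = 125 − 21k days.

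| Stopped after cycle | Days still counted as *Placebo* | Share of 126 days |
|---|---|---|
| 1 | 104 | 83% |
| 2 | 83 | 66% |
| 3 | 62 | 49% |

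**3. Share of all *Placebo* time.** Assume that a share p of placebo-first patients stop at Week 6 after a last infusion at Week 3, stay to Week 18 and never receive Panzyga, and that the rest contribute 9 weeks each. The share after withdrawal is 12p / [9(1 − p) + 18p].

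- p = 5%: 0.6 / 9.45 = 6.3%
- p = 10%: 1.2 / 9.9 = 12.1%
- p = 20%: 2.4 / 10.8 = 22.2%

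This is all time after withdrawal. Only the unknown part after immunoglobulin carries the mechanism described here.

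**4. Dilution of the contrast.** Let r be the share of placebo-first patients given non-study IVIG before any Panzyga, p0 the placebo risk, and p1 the immunoglobulin risk, taken as equal to the Panzyga risk. All three are assumptions. The apparent placebo risk is (1 − r)p0 + r[1 − (1 − p0)(1 − p1)] = p0 + r·p1(1 − p0). With p0 = 20% and p1 = 50%, it is 0.20 + 0.40r:

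| r | Apparent placebo risk | Risk difference (true 30 points) | Risk ratio (true 2.50) |
|---|---|---|---|
| 5% | 22% | 28 | 2.27 |
| 10% | 24% | 26 | 2.08 |
| 20% | 28% | 22 | 1.79 |
| 30% | 32% | 18 | 1.56 |

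The fraction of the true difference lost is r·p1(1 − p0)/(p1 − p0). This is 1.33r for 20% vs 50%, 1.40r for 30% vs 60% and 1.47r for 2% vs 6%. Across the three pairs the loss is about 7% at r = 5%, 13–15% at 10%, 27–29% at 20% and 40–44% at 30%.

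**The case against.** The strongest reply is that little is lost. Safety is exploratory and descriptive. SAP 11.1 lists every event and requires narratives for SAEs, TEEs and HTRs. Concomitant medication is recorded with dates (protocol Table 4) and summarised (SAP 9.3). SAP 8.4 itself expects further variables and flags. A reviewer could therefore find each event and see what preceded it. That stands, and it limits the harm. It does not correct the comparative tables, which follow the group definitions.

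The premise can also be questioned. Other immunoglobulin is forbidden, standard of care is not specified as IVIG, and no frequency is given. Protocol 3.3.1 says that patients with clinically important deterioration are discontinued from the study with a termination visit, which would end observation. This conflicts with 4.3.2, and the passages must be reconciled. It does not remove the explicit case in 4.3.2 of a patient followed after non-Panzyga IVIG.

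For Panzyga-first patients stopped before saline, SAP 11 already reports separately the events that start more than 21 days after the last Panzyga dose, for the whole (Panzyga – Placebo) sequence, with a medical review. That largely covers them in substance, and what remains is a wording gap. Finally, protocol 9.2.3 (Safety Analysis Plan) is blacked out, so a supplementary rule there cannot be excluded.

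A reader might infer three stronger things, which the documents do not support:

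- *That Panzyga harm is hidden.* The misplaced events follow another product, and no event leaves the *Panzyga* column.
- *That the error always favours Panzyga.* The second-period *Panzyga* window is open-ended too, so events after another immunoglobulin can be charged to Panzyga. The same holds within 21 days of Panzyga in the first period.
- *That the suspension rule in protocol 6.2.2 is weakened.* That rule counts events per infusion by randomization arm and does not refer to the SAP 8.4 groups.

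**Conclusion.** The gap is real on the readable text. SAP 8.4 does not say where a patient belongs once study drug has stopped or non-study immunoglobulin has been given. For placebo-first patients given such immunoglobulin before crossover, its wording files later events as placebo events.

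The consequence is dilution of the Panzyga-placebo contrast: about 7% of the true risk difference if 5% of placebo-first patients are affected, and 40–44% if 30% are. These figures rest on the assumed risks, and on an affected patient carrying the full placebo risk plus a full Panzyga-level risk. The true share is unknown and may be small. It is also unclear whether Panzyga given outside the study would close the *Placebo* window, since the SAP does not say whether it means study product only.

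This is a definition to correct before database lock. It is not evidence that the safety conclusion would be wrong.

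**What to change.** In SAP 8.4:

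- End *Placebo* at the earliest of the first Panzyga administration, the first non-study immunoglobulin (or plasma exchange or other immunomodulator), or 21 days after the last placebo infusion when study drug is permanently stopped. State whether Panzyga here means study product only.
- Keep every event up to 21 days after the last Panzyga infusion under *Panzyga*, whatever other therapy is given, and flag those that follow non-study immunoglobulin. Cutting this window at other therapy would take events soon after Panzyga out of the Panzyga column.
- End the second-period *Panzyga* group at the later of 21 days after the last Panzyga infusion and the first non-study immunoglobulin. If none is given, the window stays as it is now.
- Put all later events in a fourth column, *After study-drug withdrawal / non-study therapy*. It includes Panzyga-first patients stopped before any saline, from day 22.
- State whether the same closing events apply to *Placebo after Panzyga*, which also runs to the end of observation.

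Leave the protocol 6.2.2 counts unchanged. Reconcile protocol 3.3.1 with 4.3.2 on whether deteriorating patients remain in the study, since this decides how long the windows can run.

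The cost is SAP wording, one extra column and slightly less follow-up in the placebo column. The therapy dates needed are already collected in the eCRF.

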9.1. Disposition of Patients and Withdrawals

All subjects screened for the study will be accounted for. For screening failures the reasons for not being enrolled in the study will be listed and summarized.

For all patients enrolled in the study, descriptive summaries of population data will be provided overall and by randomized treatment group; these will include

- The number and percent of patients in each analysis population, overall, by randomized treatment group, and by the variables used for stratification (prophylactic use of antibiotics, PANDAS disease subtype).
- Number of patients enrolled, randomized, treated, and the number of completers
- Study withdrawals by reason of withdrawal

Individual patient assignments to the analysis populations will be listed, including the reasons for any exclusion from an analysis population.

9.2. Protocol Deviations

Protocol deviations will be checked on complete data for all patients prior to defining the analysis populations. The final decision regarding inclusion/exclusion of patients from the analysis sets will be made based on data listings and reports during data review meetings before database lock, data release and final analysis, applying the definitions in section 7.

Major/important protocol deviations will be summarized by type of deviation. All individual protocol deviations will be listed.

9.3. Demographics and Other Baseline Characteristics

Descriptive summaries of the demographic and other baseline characteristics will be completed for the populations specified below, overall and by randomized treatment group; these include:

- Demographics [REDACTED]
(ITT/FAS, PP)
- Medical History (ITT/FAS)

Medical history will be coded with the Medical Dictionary for Regulatory Activities (MedDRA, according to the version specified in the Data Management Plan). Incidences of findings in medical history will be summarized by MedDRA system organ class and preferred term

- Prior and Concomitant Medications (ITT/FAS)

Medications will be coded using the WHO Drug Dictionary (according to the version specified in the Data Management Plan). Incidences of prior and concomitant medications will be summarized by ATC level 2 and ATC level 4

- Baseline Physical Examination (ITT/FAS)
- Baseline CY-BOCS (ITT/FAS)

9.4. Measurement of Treatment Compliance

The following parameters will be listed and summarized for each treatment group, per patient and/or per infusion:

- [REDACTED]
- [REDACTED]
- [REDACTED]
- [REDACTED]

Deviations from the planned treatment schedule will be summarized by counting the number of infusions that deviate from the scheduled intervals by more than the allowed intervals, and by listing all such cases individually.

Property of Octapharma. Do not copy or distribute without written permission.

A document page with most content redacted by black bars. A large watermark 'Property of [redacted] not to be distributed without written permission' is diagonally across the page.

Proprietary and Confidential - Do Not Copy or Distribute Without Written Permission.

[figure not shown]
10.3. Exploratory analyses

The impact of the stratification variables mentioned in section 4.3 on the primary and secondary endpoints will be assessed in an exploratory manner.

10.3.1. Pharmacokinetics

Blood for the determination of IgG in plasma will be sampled at the following times:

- [REDACTED]
- [REDACTED]
- [REDACTED]

10.3.2. Correlation between CY-BOCS and CGI-I

The correlation analysis between CY-BOC and CGI-I will be performed based on ITT Population for the following exploratory endpoints:

- [REDACTED]
- [REDACTED]
- [REDACTED]
- [REDACTED]

10.3.3. Pediatric Patients with PANs improvement

PANS improvement will be defined as improvement of PANS symptoms based on CGI-I ratings at Week 9 since Week 3, and at Week 18 since Week 12. Patient will be evaluated as PANS improvement if the CGI-I score is 3 (Minimally Improved) or better at the evaluated visit.

The descriptive statistics (n and percentage %) for patients with PANS improvement will be summarized by treatment groups at Week 9 and Week 18.

not

11. Safety and Tolerability Analyses

The safety analysis will comprise descriptive statistics, tabulations and listings of all adverse events (AEs), safety laboratory results, and physical examination findings. The safety analysis will be made with the FAS, including all randomized patients who received at least part of one infusion of Panzyga or placebo. In the event that a patient received the wrong study drug (i.e. did not take the randomized study drug), the actual treatment will be used for safety analyses.

To account for the cross-over follow-up phase in this study, safety tabulations will differentiate between 3 patients groups according to their treatment status as defined in section 8.4 above.

In particular, AEs in patients with treatment sequence (Panzyga – Placebo) that start more than 21 days after the last administration of Panzyga will be reported separately, and an additional medical review will be performed to identify any possible signal of events with long latency.

11.1. Adverse Events

All reported AEs will be coded according to MedDRA.

All AEs with first onset or worsening during the treatment period, i.e. after first IMP administration, are accounted for in the analysis.

In general AE frequency tables will feature columns for each treatment group (as defined in section 8.4) and a total column in a side-by-side fashion.

All reported events will be listed and tabulated in full detail; in particular the following key figures will be presented:

- Total number of AEs reported by severity and overall
- Number of related AEs by severity and overall
- Number of TEEs and HTRs
- Number of SAEs
- Number of AEs leading to withdrawal
- Infusional AEs (AEs that occur during or within: (a) 1 hour, (b) 24 hours, and (c) 72 hours following an infusion, regardless of other factors that may impact the causality assessment

Narratives will be prepared describing each death, other SAEs, and other significant AEs that are judged to be of special interest because of clinical importance, including all TEEs and HTRs reported.

11.2. Clinical Laboratory Evaluations

All laboratory data will be converted to standard units during the Data Management process. The laboratory data will be listed with suitable flags indicating abnormal values (L=Lower than reference range, H=Higher than reference range).

Summary statistics for the laboratory values as well as their changes from baseline will be tabulated for all laboratory parameters. The tables on changes in lab parameters will again feature columns for each treatment group as defined above and a total column in a side-by-side fashion.

